6.1.1.1. Phase 1a: Dose-Limiting Toxicity Observation

For the 21-day Phase 1a DLT observation period, the following criteria will be used to determine the progress of the study:

- If none of the initial 3 patients within a dose schedule develops a DLT, Expansion Phase 1b will start.
- If 1 of the initial 3 patients within a dose schedule develops a DLT, 3 additional patients will be added.
- If ≤ 1 of 6 patients within a dose schedule develops a DLT, Expansion Phase 1b will start.
- If 2 or more patients develop a DLT, enrollment will stop and an alternative dose level may be considered (in which case the protocol would be amended).

No intra-patient dose escalation or reduction is allowed during DLT observation. For the purpose of patient management, DLTs will lead to dose interruption during the observation period. Dose modifications will be allowed after the observation period.

For either group, if dropouts, dose interruptions, or reductions occur that result in a patient being nonevaluable for DLTs (“evaluable” is defined in Section 6.7), additional patients will be enrolled to achieve the minimum of 3 evaluable patients. The need for patient replacement will be determined based on consultation with the investigator and Lilly CRP/clinical research scientist (CRS). Patients who withdraw from the study during the DLT period for reasons other than a DLT may be replaced within the same dose level.

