6.7. Treatment Compliance

The study medication will be administered only at the investigational sites by the authorized study personnel. As a result, treatment compliance is ensured.

During Phase 1a, DLT-evaluable population is defined as all enrolled patients in DLT Phase 1a who either completed 21 days of observation or discontinued study treatment or study participation before completing 1 cycle due to a DLT.

Any patient who discontinued from the study before completing safety monitoring for the 21-day DLT observation period for any other reason than a DLT will be considered non-evaluable for DLT assessment.

Patients who are not evaluable for pharmacokinetics, but who complete 1 cycle of therapy, may be replaced upon consultation with the investigator(s) and the Lilly CRP/CRS to ensure adequate PK data, unless accrual to that cohort has stopped due to a DLT.

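### DLT-evaluability in Section 6.7 depends on why a patient left, not on whether a DLT occurred, so an observed DLT can be lost from the 3+3 count

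*Protocol*

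**What the plan says.** **Who is evaluable (Protocol 6.7).** The DLT-evaluable population is the Phase 1a patients "who either completed 21 days of observation or discontinued study treatment or study participation before completing 1 cycle due to a DLT". A patient who leaves the study before the 21 days are up "for any other reason than a DLT will be considered non-evaluable for DLT assessment". Neither sentence mentions a patient who has had a DLT and leaves for some other reason.

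**What follows a DLT (Protocol 6.1.1.1).** "DLTs will lead to dose interruption during the observation period". Treatment is interrupted, so the patient is not automatically off treatment or off study.

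**Top-up and replacement (Protocol 6.1.1.1).** The section points to 6.7 for the meaning of evaluable. When patients are not evaluable, "additional patients will be enrolled to achieve the minimum of 3 evaluable patients". It adds: "Patients who withdraw from the study during the DLT period for reasons other than a DLT may be replaced within the same dose level". It also says: "The need for patient replacement will be determined based on consultation with the investigator" and the sponsor's clinical staff.

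**The count (Protocol 6.1.1.1).** "If 1 of the initial 3 patients within a dose schedule develops a DLT, 3 additional patients will be added". At most 1 of 6 opens the expansion, and 2 or more patients with a DLT stops enrollment. These rules speak of patients, not evaluable patients. Section 4.1.2 likewise refers to the number of DLTs without restriction.

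**The SAP.** Section 5.1.1 sizes Phase 1a in DLT-evaluable patients, but Section 5.2.1.7 defines no such set.

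**The concern.** Non-evaluability in a 3+3 design exists to deal with patients whose DLT status is unknown because they were not observed for long enough. Once a DLT has been seen, the status is known and later events cannot change it. Section 6.7 tests something else, namely the reason for leaving.

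The affected patient is one with a DLT, dosing interrupted, who then leaves the study before Day 21 through consent withdrawal, loss to follow-up or unrelated death. Section 6.7 calls that patient non-evaluable for DLT assessment, while the counting rules in 6.1.1.1 read as though the DLT still counts.

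The 3+3 result decides whether expansion cohorts open: 15 + 25 + 25 = 65 patients on Schedule 1 and 15 + 25 + 25 + 25 = 90 on Schedule 2. With three to six patients per schedule, one DLT is enough to change the outcome. Dropping a DLT can move the decision only toward expansion.

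**Working it through.** **1. The plan's own figure.** Two schedules with at most 3 + 3 patients each gives 2 × 6 = 12, which matches the stated maximum of DLT-evaluable patients. The documents give no operating characteristics for the 3+3 rule.

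**2. The provisions applied to three patients.**

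| Patient | 6.7, evaluable sentence | 6.7, non-evaluable sentence | 6.1.1.1 go/stop rules |
|---|---|---|---|
| DLT, interrupted, observed to Day 21 | Evaluable | Does not apply | Counted |
| DLT, interrupted, withdraws consent on Day 15 | Not evaluable | Non-evaluable | Counted |
| Stops treatment for a DLT on Day 8, withdraws consent for another reason on Day 15 | Evaluable | Non-evaluable | Counted |

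In the second row, 6.7 and 6.1.1.1 disagree. In the third row the two sentences of 6.7 disagree with each other, because the first accepts "discontinued study treatment or study participation before completing 1 cycle due to a DLT" while the second looks only at why the patient left the study.

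**3. One affected patient in the first three.** Let p be the true DLT probability. The documents give no value, so p is an assumption. One of the first three has a DLT and leaves; the other two are clean.

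- DLT counted: 1 of 3, add three, all must be clean. P(expand) = (1−p)³. At p = 0.33: 0.67³ = 0.301.
- Dropped and replaced: a clean replacement gives 0 of 3 and expansion; a replacement with a DLT gives 1 of 3, and three more must be clean. P(expand) = (1−p) + p(1−p)³. At p = 0.33: 0.67 + 0.33 × 0.301 = 0.769.

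| p | Counted | Dropped and replaced |
|---|---|---|
| 0.20 | 0.512 | 0.902 |
| 0.33 | 0.301 | 0.769 |
| 0.40 | 0.216 | 0.686 |
| 0.50 | 0.125 | 0.562 |

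**4. One affected patient in the second three.** There was already a DLT in the first three, and the other two of the second three are clean. Counted, this is 2 of 6 and a certain stop. Dropped and replaced, expansion needs only a clean replacement: 1−p = 0.67 at p = 0.33.

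**5. Average effect, illustrative only.** The full rule gives P(expand) = (1−p)³ + 3p(1−p)²(1−p)³. At p = 0.33: 0.301 + 0.134 = 0.434. Suppose a fraction q of DLT patients leaves for another reason and all of them are dropped and replaced, with no early exit among the rest. The DLT rate among evaluable patients becomes p(1−q)/[p(1−q) + (1−p)].

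| q (assumed) | Rate among evaluable, p = 0.33 | P(expand) |
|---|---|---|
| 0 | 0.330 | 0.434 |
| 0.10 | 0.307 | 0.480 |
| 0.20 | 0.283 | 0.530 |

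At p = 0.40 the corresponding chances are 0.309, 0.351 and 0.401.

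**6. Equal exit in both groups.** If 10% of patients leave early whether or not they had a DLT, dropping them all leaves the rate at p and P(expand) at 0.434. The right comparator then counts every DLT and replaces only DLT-free dropouts: 0.33/(0.33 + 0.67 × 0.90) = 0.354, giving P(expand) of about 0.39. The direction is unchanged.

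**The case against.** A reader might infer that the protocol removes such a DLT from the 3+3 decision. The documents do not say that, and the case against that reading is good.

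- The go/stop rules in 6.1.1.1, and Section 4.1.2, are not limited to evaluable patients. Topping up to a floor of three can be read as giving 1 DLT among 4 treated, which erases nothing.
- Replacement is permitted rather than required, and is settled by consultation.
- Protocol 9.5 summarizes every patient with a Cycle 1 DLT. Protocol 9.8 and SAP 5.3.15 base the move to expansion on all the data.
- The affected group is narrow. The exclusion covers leaving the study. A patient who stops treatment for progression enters about 30 days of safety follow-up (4.1.3) and can still complete 21 days. Withdrawal required by a possibly related toxicity is an example of a DLT under 6.1.1.1.1, item 4a, and a related death is a DLT under item 3. Entry requires ECOG 0 or 1 and a life expectancy of at least 3 months.
- The exit fractions have no source in the documents.
- The amendment summary (Attachment 9) says Schedule 2 DLT observation was complete, so new wording cannot alter that decision.

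All of this stands as a limit on the claim. It does not resolve the conflict. One provision calls the patient non-evaluable for DLT assessment, another appears to count the DLT, and none gives precedence. Consultation after the toxicity is known leaves open a choice that the counting rule should settle in advance. A safety summary reports the DLT but does not apply the go/stop rule.

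**Conclusion.** The point holds as an unreconciled conflict with a real consequence. Read literally, Section 6.7 makes a patient with an observed DLT non-evaluable if that patient leaves the study before Day 21 for another reason, and 6.1.1.1 permits replacement. The counting rules in 6.1.1.1 point the other way. A DLT can be lost; the stronger claim that it must be lost is not supported.

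The firmest measure of size is the single-patient case: a chance of expanding of 0.30 against 0.77. It needs an assumed true DLT rate (0.33) and a case in which the conflict arises and is resolved by dropping the patient, but no exit rate. The average shift from 0.434 to 0.480 or 0.530 rests on assumed exit fractions of 10% and 20% and should not be read as an estimate. The likely frequency is low, because few routes out of the study within 21 days qualify.

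At this amendment the practical reach is the Schedule 1 decision, with 65 expansion patients behind it.

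**What to change.** - **Protocol 6.7, definition.** Make a Phase 1a patient DLT-evaluable if either a DLT occurs at any time in the 21-day window, whatever happens to the patient afterwards, or the window is completed with no DLT.
- **Protocol 6.7, non-evaluable sentence.** Confine it to patients who leave the study early without having had a DLT.
- **Protocol 6.1.1.1, top-up and replacement wording.** Apply the same limit, and state that a patient with a DLT is not replaced for the purpose of the count.
- **SAP 5.2.1.7.** Add the DLT-evaluable set with the same definition, since SAP 5.1.1 already uses the term.

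The cost is a few sentences across the two documents. No patients, visits or procedures are added, and the go/stop thresholds do not change. For Schedule 2, whose observation period had ended, it is enough to confirm in the study report that no patient with a DLT was classed as non-evaluable or replaced.

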6.8. Lifestyle and/or Dietary Requirements

6.8.1. Diet

Patients should maintain a normal diet unless modifications are required to manage an AE such as diarrhea, nausea, or vomiting.

6.8.2. Contraception

Based on ramucirumab's mechanism of action, it is likely that ramucirumab will inhibit angiogenesis and may potentially result in adverse effects during pregnancy and postnatal development.

Pembrolizumab may have adverse effects on a fetus in utero. Furthermore, it is not known if pembrolizumab has transient adverse effects on the composition of sperm.

Therefore, 1) non-pregnant, non-breast-feeding women may only be enrolled if they are willing to use a highly effective method of birth control or are considered to be of non-childbearing potential and 2) only men may be enrolled who use a reliable method of birth control, or who are sterile (including confirmed vasectomy) and do not donate sperm (Section 5.1).

For female patients, non-childbearing potential (by other than medical reasons) is defined as any one of the following:

- ≥ 45 years of age and has not had menses for greater than 2 years
- Amenorrheic for < 2 years without a hysterectomy and oophorectomy and a follicle-stimulating hormone (FSH) value in the postmenopausal range upon pretrial (screening) evaluation (FSH level >40 mIU/mL)
- At least 6 weeks following surgical bilateral oophorectomy or tubal ligation with or without hysterectomy. Documented hysterectomy or oophorectomy must be confirmed with medical records of the actual procedure or confirmed by an ultrasound. Tubal ligation must be confirmed with medical records of the actual procedure; otherwise, the patient must be willing to use an adequate barrier method throughout the study, starting with the screening visit through 120 days after the last dose of study treatment.
- not heterosexually active for the duration of the study

A “highly effective method of birth control” is defined as one that results in a low failure rate (that is, $<1\%$ per year) when used consistently and correctly, such as implants, injectables, combined oral contraceptives, some intrauterine contraceptive devices, sexual abstinence, or a vasectomized partner.

Two birth control methods are preferred, and can be either 2 barrier methods or a barrier method plus a hormonal method to prevent pregnancy. The following are considered adequate barrier methods of contraception: diaphragm, condom (by the partner), copper intrauterine device, sponge, or spermicide as per local regulations or guidelines.

Appropriate hormonal contraceptives will include any registered and marketed contraceptive agent that contains an estrogen and/or a progestational agent (including oral, subcutaneous, intrauterine, or intramuscular agents). For patients using a hormonal contraceptive method, information regarding pembrolizumab and its potential effect on the contraceptive should be addressed.

Patients should start using birth control from study Visit 1 throughout the study period up to 120 days after the last dose of study treatment.

Patients should be informed that taking the study medication may involve unknown risks to the fetus (unborn baby) if pregnancy were to occur during the study. If there is any question that a patient will not reliably comply with the requirements for contraception, that patient should not be entered into the study.

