- [11] For male patients, are sterile (including vasectomy confirmed by post-vasectomy semen analysis) or agree to use a reliable method of birth control and to not donate sperm during the study and for at least 120 days following the last dose of study treatment
 - Note: Abstinence is acceptable if this is the established and preferred contraception for the patient.
- [12] For female patients, are surgically sterile, are postmenopausal, or agree to use a highly effective method of birth control (2 methods preferred) during the study and for 120 days following the last dose of study treatment
 - Note: A "highly effective method of birth control" is defined in Section [6.8.2](#).
- [13] If female and of childbearing potential, must have a negative serum or urine pregnancy test within 7 days prior to enrollment.
 - Note: Non-childbearing potential (by other than medical reasons) is defined in Section [6.8.2](#).
 - Note: Abstinence is acceptable if this is the established and preferred contraception for the patient.

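### Sexual inactivity during the study counts as non-childbearing potential, so a woman able to conceive can reach her first dose with no required pregnancy test

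*Protocol*

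**What the plan says.** Protocol Section 6.8.2 states that "non-childbearing potential (by other than medical reasons) is defined as any one of the following" and then lists four items: an age and menses rule; recent amenorrhea with "a follicle-stimulating hormone (FSH) value in the postmenopausal range upon pretrial (screening) evaluation"; prior oophorectomy or tubal ligation, with documentation rules such as "Documented hysterectomy or oophorectomy must be confirmed with medical records of the actual procedure or confirmed by an ultrasound"; and "not heterosexually active for the duration of the study". The last item stands alone, with no physiological condition and no check attached.

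The same section then lists highly effective birth-control methods, ending with "some intrauterine contraceptive devices, sexual abstinence, or a vasectomized partner". Sexual inactivity therefore appears twice, once as a reason for being unable to conceive and once as a contraceptive method.

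The eligibility test is in Section 5.1, criterion 13: "If female and of childbearing potential, must have a negative serum or urine pregnancy test within 7 days prior to enrollment". A note under that criterion refers to Section 6.8.2 for the meaning of non-childbearing potential. A second note says "Abstinence is acceptable if this is the established and preferred contraception for the patient". The pregnancy-test row of Attachment 1 and footnote c of Attachment 3 limit the test to women of childbearing potential in the same way.

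**The concern.** A baseline pregnancy test is there to find a pregnancy that exists when the patient enters. A statement about what she will do from then on says nothing about that. If the statement alone moves her out of the tested group, the check is dropped for a woman whose physiology gives no ground for dropping it.

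What is at stake is fetal exposure. Section 6.8.2 accepts that ramucirumab's mechanism may cause harm in pregnancy and after birth, and that pembrolizumab may harm a fetus. None of exclusion criteria 14 to 47 names pregnancy, so criterion 13 is the only eligibility item that tests for it.

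**Working it through.** No arithmetic applies beyond counting required tests. The check is to take one woman, premenopausal and unsterilized, who says she will not be heterosexually active on study, and follow her through each provision.

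| Place in the protocol | What it decides | Result for this woman |
|---|---|---|
| Section 6.8.2, non-childbearing list | Any one of four items suffices | Meets the fourth item, so classed as non-childbearing |
| Section 5.1, criterion 13 and its reference to 6.8.2 | Test required only if of childbearing potential | Not required |
| Attachment 1, pregnancy-test row | Same condition | Not required |
| Attachment 3, footnote c | Same condition | Not required |
| Section 6.8.2, method list | Abstinence is a highly effective method | Can instead be classed as a contraceptive user |
| Section 5.1, criterion 12 | Surgically sterile, postmenopausal, or agrees to a highly effective method | Neither of the first two, so enters as a method user |
| Section 5.1, note to criterion 13 | Abstinence is a form of contraception | Treated as able to conceive |

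1. **Required tests before the first dose.** Classed by the fourth item: 0. Classed as a contraceptive user: 1, within the 7 days before enrollment. The woman and her conduct are the same; only the paragraph that the site applies differs.

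2. **Does any other text restore the test?** Section 6.8.2 says "non-pregnant, non-breast-feeding women may only be enrolled if they are willing to use a highly effective method of birth control", and the sentence goes on to offer non-childbearing potential as the alternative. It makes not being pregnant a condition of enrollment, but names no way of establishing it for a woman outside the tested group. Attachment 1 allows testing at other times where local rules require it, but places that in the treatment period, after the first dose. Baseline history, examination and imaging of chest, abdomen and pelvis (Section 8.1.1) remain, but none is a pregnancy test. Nothing found closes the gap.

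3. **Is the exemption consistent with the rest of the plan?** No. Criterion 12, the note to criterion 13 and the method list all lead to the same place: a woman who is neither sterile nor postmenopausal can conceive, and abstinence is a method she may use. The fourth item is the one text that says otherwise.

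**The case against.** The strongest reply is criterion 12. Every inclusion criterion must be met, and criterion 12 offers three routes, none of which is sexual inactivity as such. This woman can enter only by agreeing to a highly effective method, with abstinence as that method. She is then a contraceptive user, and a careful site would test her. On this view the fourth item is a drafting slip that the criteria override.

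Part of this stands. The criteria taken together do favor testing, and the documents show no intention to leave such women untested. But criterion 12 does not order the test. Criterion 13 does, and it depends on childbearing potential as Section 6.8.2 defines it. A site can accept her agreement to abstain under criterion 12, class her as non-childbearing under criterion 13, and comply with both as written.

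Two stronger readings might be inferred, and neither is supported:

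- **That the fourth item leaves a contraceptive gap after treatment, because it covers only the study.** Criterion 12 binds her for 120 days after the last dose whatever the fourth item says, and Section 6.8.2 repeats that period.
- **That the other three items all rest on facts fixed at entry, with the fourth the only one that turns on future conduct.** The third item also accepts a promise: where a tubal ligation cannot be confirmed from records, willingness to use barrier contraception suffices. The objection to the fourth item is that it has no physiological or surgical basis at all.

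It can also be said that the risk is small. Where abstinence is long established, pregnancy at entry is remote, and Section 6.8.2 keeps out any patient whose contraceptive compliance is in doubt. Both points are fair and limit the weight of the concern. Neither helps where abstinence begins at or shortly before entry.

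**Conclusion.** The point holds on the literal text. A premenopausal, unsterilized woman classed under the fourth item has 0 required pregnancy tests before the first dose, against 1 if the same conduct is treated as contraception. It would be wrong to go further and say that pregnant women are eligible, since Section 6.8.2 limits enrollment to women who are not pregnant. What is missing is the check that would show it.

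The conclusion assumes that a site applies the fourth item as written and does not test by local habit. The documents do not size the group. It is probably small, and the risk lies mainly with women whose abstinence is recent. Sample size, power and efficacy analyses are unaffected. The change is still worth making: the possible harm is serious, and the safeguard is a test that the protocol already schedules for other women.

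**What to change.** Delete the fourth item from the non-childbearing list in Section 6.8.2. No new wording is needed, because abstinence is already in the list of highly effective methods and criterion 12 already fixes the contraceptive period. Criterion 13, Attachment 1 and Attachment 3 then apply to her as they stand. A woman who is not heterosexually active, including one with female partners only, uses abstinence as her method and need not adopt another.

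The cost is one deleted line and a local urine or serum test for a few more women. The deletion does not touch the unconfirmed-ligation branch of the third item, which is a separate matter.

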6.9. Concomitant Therapy

A list of restricted and excluded concomitant therapies and exceptions is provided in [Attachment 7](#). All premedication, supportive care, and concomitant medication must be reported on the CRF at each visit.

6.9.1. *Supportive Care*

Patients should receive appropriate supportive care measures as deemed necessary by the treating investigator. For both study drugs, specific AEs have been identified based on past data for special monitoring and, when necessary, supportive care. For ramucirumab, these are referred to as Adverse Events of Special Interest (AESI).

See [Table JVDF.4](#) and [Table JVDF.5](#) for dose reductions (ramucirumab only), delays, or discontinuations for AEs considered to be at least possibly related to study treatment (pembrolizumab or ramucirumab).

6.9.1.1. *Infusion-Related Reactions- Ramucirumab and Pembrolizumab*

Infusion-related reactions (IRRs) have been identified as events of interest for both ramucirumab and pembrolizumab. In the event of an IRR, blood samples will be collected for both PK and immunogenicity analysis for each drug at the following time points: (i) as close as possible to the onset of the IRR, (ii) at the resolution of the IRR, and (iii) 30 days following the IRR.

IRRs may occur during or following ramucirumab or pembrolizumab administration. Patients should be closely monitored for signs and symptoms indicative of an IRR from the initiation of the infusion in an area where resuscitation equipment and other agents (such as epinephrine and corticosteroids) are readily available.

Signs and symptoms usually develop during or shortly after infusion and generally resolve within 24 hours. Symptoms of IRRs include rigors/tremors, back pain/spasms, chest pain and/or tightness, chills, flushing, dyspnea, wheezing, hypoxia, and paresthesia. In severe cases, symptoms include bronchospasm, supraventricular tachycardia, and hypotension.

The first 2 cycles will require a 1-hour observation period i) between ramucirumab and pembrolizumab administration, and ii) after pembrolizumab infusion. For all cycles thereafter, no observation period will be required unless clinically indicated. If the patient shows no evidence of an IRR with the first 2 cycles of each study drug, no observation period is required for subsequent cycles, unless clinically indicated. In the event an IRR occurs thereafter, the 1-hour observation should be reinstated.

6.9.1.1.1. *Infusion-Related Reactions-Ramucirumab*

[Table JVDF.4](#) presents ramucirumab dose modification and supportive care guidelines for patients who experience an IRR associated with ramucirumab.

For the first 2 ramucirumab infusions, measure blood pressure and pulse at the following time points: (i) within 15 minutes prior to the infusion, (ii) after completion of the infusion, and (iii) at the end of the 1-hour post-infusion observation period. For all subsequent infusions of ramucirumab, measure blood pressure and pulse prior to the infusion. Measure other vital signs as clinically indicated.

